15.5 Sample Size Calculation

We did two sets of power analysis to account for the drinking and smoking endpoints in our proposed study. Importantly, because smoking outcomes are based mostly on dichotomous variables, power estimates for these outcomes drive the numbers needed for this comorbid alcohol- and nicotine-dependent cohort. Hence, it is important to have adequate power for the smoking outcomes even though this will result in a superfluous level of power for the drinking outcomes.

First, for the smoking outcomes, we did a power analysis by comparing the two-sample difference in nicotine abstinence using SAS Proc POWER. We have estimated power based upon our ability to detect a difference in the percentage of smoking abstinence between the treatment groups. Because the comparisons of the topiramate groups with one another (i.e., high vs. low) and with placebo are experimental, we chose to calculate power to detect the effect size of therapeutic treatments typical of the smoking cessation literature. We chose to calculate power based on our estimates of the percentage of smoking abstinence in the pivotal study by Jorenby et al.,[72] where bupropion was compared with placebo in a 9-week randomized, controlled clinical trial. In that study, the TQD occurred at the end of the first week of double-blind treatment. As a conservative measure, we have accepted the subject numbers for these two groups for the present study to represent the comparison of the low-dose topiramate vs. placebo or the high-dose vs. low-dose topiramate. Thus, we have assumed that the difference between low-dose topiramate and placebo would be similar to that between high- and low-dose topiramate. Since there are 3 pairwise comparisons between the three arms, we will adopt Bonferroni's adjustment and take alpha level as $0.05/3 = 0.017$.

From Figure 1 in Jorenby et al.,[72] the continuous prevalence rate of smoking abstinence at 18 weeks is approximately 10% for placebo and 28% for bupropion. Using these numbers, we find that 98 subjects in each arm (294 in total) are needed to achieve a power of 0.80. If we observe a similar effect to that in the preliminary study we will be operating under even increased power.

For the drinking outcome, we based the power calculation from data obtained in a previous multi-site randomized controlled trial of topiramate for the treatment of alcohol dependence.[5] We observed that the slope of PHDD for the topiramate group declined faster than that for the placebo group by 0.014 per week, with a standard error of 0.003. We anticipate that the weekly PHDD will have this similar variability in the proposed trial. We have assumed that the low and high doses of topiramate will have a similar trajectory but with the high dose being more efficacious.

The null hypothesis is that there is no difference in the declining rate in weekly PHDD between low-dose topiramate, high-dose topiramate, and the placebo group. Power was then obtained by the probability that the non-centrality parameter is

greater than the critical value in the F-distribution with the numerator and denominator degrees of freedom from the mixed-model results. Since there are 3 pairwise comparisons between the three arms, we will use Bonferroni's adjustment and take alpha level as $0.05/3 = 0.017$. We find that 76 subjects in each of the treatment arms (a total of 228 subjects in 3 arms) will yield a power of 80%. Hence, this study will be operating under increased power for the primary efficacy variable on drinking outcome. The technical details of the power calculations for mixed models can be found in Littell et al.[73] (Chapter 12). The figure above shows the power curve for different sample sizes.

Since we already accounted for dropout in the mixed model for the multi-site study, no additional measure to address the attrition rate is necessary as long as the weekly dropout rate (i.e., not the total dropout) in the present study is similar to that in the previous trial.

After considering both sample sizes, we chose the larger value, 98 subjects in each group, as our final sample size. It can fulfill our need to test our primary hypothesis.

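### Section 15.5 applies one pair of smoking abstinence rates (10% and 28%) to two contrasts that share the low-dose arm, so 0.80 power is not established for high versus low dose (about 0.59 if the two differences are both 18 points)

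*Combined protocol and SAP*

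**What the plan says.** Section 15.5 (Sample Size Calculation) states that smoking outcomes drive the sample size. Its basis is described in two ways: "We have estimated power based upon our ability to detect a difference in the percentage of smoking abstinence between the treatment groups", and "we chose to calculate power to detect the effect size of therapeutic treatments typical of the smoking cessation literature". The only rates come from a published bupropion trial, where "the continuous prevalence rate of smoking abstinence at 18 weeks is approximately 10% for placebo and 28% for bupropion". From these, "we find that 98 subjects in each arm (294 in total) are needed to achieve a power of 0.80", at a Bonferroni alpha of 0.05/3 for three pairwise comparisons.

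The section presents its use of this number as cautious: "As a conservative measure, we have accepted the subject numbers for these two groups for the present study". One number is meant to serve for either of two contrasts, since it is taken "to represent the comparison of the low-dose topiramate vs. placebo or the high-dose vs. low-dose topiramate". The linking assumption is given in the next sentence of the section: "Thus, we have assumed that the difference between low-dose topiramate and placebo would be similar to that between high- and low-dose topiramate". It adds: "If we observe a similar effect to that in the preliminary study we will be operating under even increased power". Its closing paragraph concludes that 98 per group is enough to test the primary hypothesis.

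Section 15.3 lists superiority of high over low dose, for smoking abstinence as well as heavy drinking, as the second primary hypothesis. Section 15.4 names logistic regression, adjusted for baseline, as the abstinence analysis.

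**The concern.** The power of a two-proportion test depends on both rates, not only on the gap between them. Carrying 98 per arm and 0.80 from one contrast to another therefore carries the pair 10% and 28%. The low-dose arm would have to be the 28% arm against placebo and the 10% arm against high dose.

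Reversing the anchor does not help. If 10% and 28% were low and high dose, an equal 18-point step would put placebo at 10 − 18 = −8%. An equal risk ratio of 2.8 would put it at 10/2.8 = 3.6%, not the 10% that the section gives for placebo.

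Once low dose is at 28%, a further 18 points takes high dose to 46%. Binomial variance is larger in that range, so the same gap is harder to detect. At stake is a primary hypothesis in a trial described as having 80% power. A non-significant high-versus-low result could be read as evidence that the doses are equivalent when the test had little better than an even chance of finding the assumed difference.

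**Working it through.** **Inputs (section 15.5).** Rates 10% and 28%; 98 per arm, equal allocation; alpha 0.05/3 = 0.0167 per comparison. Sidedness is not stated. I take two-sided because it reproduces 98; a one-sided test would need 83 per arm. The high-dose rates below are my assumptions, since the plan states none.

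**Formulas (pooled-variance normal approximation, unadjusted test).** With p̄ the mean of the two rates, d their difference, z₁ = 2.394 (two-sided 0.05/3) and z₂ = 0.842 (80% power):

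- n per arm = [z₁√(2p̄(1−p̄)) + z₂√(p₁(1−p₁)+p₂(1−p₂))]² / d²
- power = Φ{[d√n − z₁√(2p̄(1−p̄))] / √(p₁(1−p₁)+p₂(1−p₂))}

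**Step 1: the plan's figure, 10% versus 28%.** p̄ = 0.19; √(2 × 0.19 × 0.81) = 0.5548; √(0.0900 + 0.2016) = 0.5400.

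- n = (2.394 × 0.5548 + 0.842 × 0.5400)² / 0.18² = 98.08
- power at 98 = Φ[(0.18 × 9.899 − 1.328)/0.5400] = Φ(0.840) = 0.7996

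At the rounded alpha of 0.017, power is 0.802. The stated 98 and 0.80 reproduce.

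**Step 2: high versus low dose with an equal 18-point difference, 28% versus 46%.** p̄ = 0.37; √(2 × 0.37 × 0.63) = 0.6828; √(0.2016 + 0.2484) = 0.6708.

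- power at 98 = Φ[(1.782 − 2.394 × 0.6828)/0.6708] = Φ(0.220) = 0.587
- n for 80% = 149.27 per arm

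Power is 0.590 at alpha 0.017 and 0.588 by exact enumeration of the Pearson test. Even one-sided it is only 0.69.

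**Step 3: other meanings of similar.** Low dose at 28%, 98 per arm, two-sided 0.05/3:

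| Scale held equal | Size, from 10% vs 28% | Implied high-dose rate | Power, high vs low |
|---|---|---|---|
| Difference | 18 points | 46% | 0.59 |
| Arcsine effect size | h = 2·asin√0.28 − 2·asin√0.10 = 0.47 | 50.8% | 0.82 |
| Odds ratio | (0.28/0.72)/(0.10/0.90) = 3.5 | 57.6% | 0.97 |
| Risk ratio | 0.28/0.10 = 2.8 | 78.4% | about 1.00 |

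**Step 4: what 80% requires.** Solving the power formula for the high-dose rate against 28% gives 50.4%: a difference of 22.4 points, odds ratio 2.61.

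**Step 5: the third contrast.** High dose versus placebo on the 18-point reading, 10% versus 46%, has power above 0.999.

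**The case against.** The strongest reply is that only one of the four scales falls below 0.80. The section speaks of an effect size, and section 15.4 analyses abstinence by logistic regression, whose natural measure is the odds ratio. An odds ratio of 3.5 for both contrasts is coherent and gives 0.97. On this view the section carries over an effect, not a pair of rates, and assigns no rate to any arm of this trial.

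Part of this stands. The 0.59 is conditional, and the documents do not prove that high-versus-low power is below 0.80. But the section describes its calculation as a difference in the percentage abstinent and then calls the two differences similar, so percentage points is the plainest reading; the effect-size phrase fixes no scale. The odds-ratio reading needs 57.6% abstinence on high dose, which the plan nowhere says it expects. And the section carries over the subject number itself, which is right only for the rates that produced it.

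The claim to be conservative is fair in one sense: sizing on adjacent contrasts is more cautious than sizing on high dose versus placebo. It does not bring 0.80 to the high-versus-low contrast on the 18-point reading. The remark about increased power rests on a preliminary-study effect that the documents do not quantify. Covariate adjustment may change power, but by an amount that cannot be computed from the documents, and section 15.5 does not rely on it. Whether 98 allows for the expected 30% dropout is a separate question.

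**Conclusion.** The concern holds. The figure of 98 per arm and power 0.80 is correct for low dose versus placebo at 10% and 28%. It is not established for high versus low dose, because the plan gives no high-dose rate and no scale for similar. On the percentage-point reading, power for that contrast is about 0.59, so a true high-dose advantage of 18 points would be missed about 4 times in 10 (1 − 0.587 = 0.413). The conclusion that 98 per group suffices for the primary hypothesis holds at 80% for this smoking contrast only if high-dose abstinence is about 50.4% or more. These figures assume low dose at 28%, a two-sided unadjusted test at 0.05/3, and 98 analysed per arm.

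**What to change.** Keep 294 subjects, the hypotheses, the tests and the alpha. In section 15.5:

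- State the assumed smoking abstinence rate in each of the three arms, the scale on which the two differences are taken as similar, and that the test is two-sided, if it is.
- Report smoking power by contrast under that assumption. If the scale is percentage points: 80% for low dose versus placebo (10% vs 28%), about 59% for high versus low dose (28% vs 46%), and over 99.9% for high dose versus placebo (10% vs 46%).
- State that 80% power for high versus low dose needs about 28% versus 50.4%, a difference of 22.4 points.
- Limit the claim to be conservative, and the closing statement that the sample size suffices, to the contrasts that reach 80%.

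The cost is rewording one section, with no more patients. One stated power figure may become less favourable.

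### The flat 0.05/3 for the three arm comparisons is valid but more conservative than it needs to be; a step-down rule would recover power for the second and third comparisons at no cost in subjects

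*Combined protocol and SAP*

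**What the plan says.** Section 15.3 sets out two primary hypotheses, each covering drinking (PHDD) and smoking (continuous abstinence): that both topiramate doses beat placebo, and that the high dose beats the low dose. Within each outcome this makes three pairwise comparisons.

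The only multiplicity rule in the documents is in section 15.5. For smoking: "Since there are 3 pairwise comparisons between the three arms, we will adopt Bonferroni's adjustment and take alpha level as" 0.05/3 = 0.017. For drinking: "Since there are 3 pairwise comparisons between the three arms, we will use Bonferroni's adjustment and take alpha level as" the same value. The verbs read as a commitment. The analysis text in 15.4, which names a GLM for PHDD and logistic regression for abstinence, gives no multiplicity rule, and no simultaneous confidence intervals are planned anywhere.

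The smoking calculation takes these rates from a bupropion trial: "the continuous prevalence rate of smoking abstinence at 18 weeks is approximately 10% for placebo and 28% for bupropion". On the dose comparison, "we have assumed that the difference between low-dose topiramate and placebo would be similar to that between high- and low-dose topiramate". The result is that "98 subjects in each arm (294 in total) are needed to achieve a power of 0.80".

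**The concern.** A flat 0.05/3 treats the three nulls as if any combination of them could be true. With three arms that is not so. If placebo and low dose differ, then placebo = high and low = high cannot both hold, because together they would make placebo equal to low. Once one null is false, at most one of the other two can be true, and no further division of the 5% is needed.

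The hypotheses in 15.3 need more than one rejection. Showing that both doses beat placebo takes two, and adding high over low takes a third. Those later comparisons are where a flat Bonferroni rule gives up power. In a 294-subject trial with about 54 months of recruitment, that power is worth recovering if it costs only wording.

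**Working it through.** **Inputs.** From 15.5: rates 10% and 28%, 98 per arm, three comparisons, alpha 0.05/3 written as 0.017, power 0.80. Sidedness is not stated. Two-sided is assumed because it reproduces 98, whereas one-sided gives 83. The high-dose rate is not stated either; taking the similar difference as another 18 points gives 28% + 18% = 46%, an assumption.

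**Step 1: reproduce the plan's 98.** For two proportions with pooled variance and no continuity correction,

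n = [z(1−α/2)·√(2p̄(1−p̄)) + z(0.80)·√(p1(1−p1) + p2(1−p2))]² / (p2 − p1)².

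- p̄ = 0.19, so √(2 × 0.19 × 0.81) = 0.5548.
- √(0.10 × 0.90 + 0.28 × 0.72) = 0.5400.
- α = 0.017: z = 2.3867, and n = (2.3867 × 0.5548 + 0.8416 × 0.5400)² / 0.18² = 97.6, rounded up to **98**.
- α exactly 0.05/3: z = 2.3940, n = 98.1, rounded up to 99.

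Power at 98 is 0.802 and 0.800 respectively. The plan's figure stands for 10% against 28%.

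**Step 2: power of each comparison by alpha.** Power = Φ{[√n·(p2 − p1) − z(1−α/2)·√(2p̄(1−p̄))] / √(p1(1−p1) + p2(1−p2))}, with √98 × 0.18 = 1.7819.

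- 10% vs 28% at 0.05/3: Φ[(1.7819 − 2.3940 × 0.5548)/0.5400] = Φ(0.840) = 0.80. At 0.05: Φ(1.286) = 0.90.
- 28% vs 46% at 0.05/3: Φ[(1.7819 − 2.3940 × 0.6828)/0.6708] = Φ(0.220) = 0.59. At 0.05: Φ(0.661) = 0.75.

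**Step 3: why 5% still holds.** For two-sided equality nulls, the number of true nulls among the three is 3, 1 or 0; it cannot be 2. Shaffer's rule tests the smallest p-value at 0.05/3, stops if it fails, and otherwise tests the other two at 0.05.

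- Three true: any rejection first needs a p-value at or below 0.05/3, so the error is at most 3 × 0.05/3 = 5%.
- One true: only that one can be falsely rejected, and it is never tested above 0.05.
- None true: no false rejection is possible.

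The first step is Bonferroni's own level and later steps are looser, so every Bonferroni rejection is kept.

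**Step 4: simulation.** 1,000,000 three-arm trials per scenario, 98 per arm, pooled two-sided z-tests.

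| Rates (placebo/low/high) | Claim | Bonferroni | Holm | Shaffer |
|---|---|---|---|---|
| 10/28/46% | low vs placebo | 0.81 | 0.90 | 0.91 |
| 10/28/46% | both doses vs placebo | 0.81 | 0.90 | 0.91 |
| 10/28/46% | high vs low | 0.59 | 0.74 | 0.74 |
| 10/28/46% | all three | 0.43 | 0.65 | 0.66 |
| 10/28/28% (alternative assumption) | both doses vs placebo | 0.70 | 0.76 | 0.83 |

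The simulated 0.81 sits slightly above the 0.80 of step 2 because exact binomial sampling differs a little from the normal approximation. High vs placebo at 10/28/46% is 0.9998 under every rule in the table. The chance of at least one rejection is also the same under all three (0.9998 at 10/28/46%, 0.924 at 10/28/28%).

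**Step 5: error and dominance.** With all arms equal, familywise error was 4.1% (all at 10%) or 4.4% (all at 28%), identical for the three rules. With one true null it was 1.6–1.7% for Bonferroni, 3.7–4.0% for Holm and 5.0–5.2% for Shaffer; the slight excess over 5% is the large-sample z-test on discrete data, not the stepping. Holm and Shaffer lost no Bonferroni rejection in any scenario. A rule of an omnibus test followed by 0.05 did lose some, in up to 0.5% of trials.

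**The case against.** The strongest reply is that no error has been shown. Bonferroni is valid, 98 per arm reproduces, and sizing at 0.05/3 is also right for a stepwise rule, whose first step is that level. All of this stands. The point is an inexpensive improvement.

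A reader might infer that the flat rule gives up power for nothing. The documents do not support that. Stepping spends error that Bonferroni leaves unused: with one true null, about 1.6% becomes the nominal 5%. It also gives up simple simultaneous intervals that match the tests, although the plan does not ask for any.

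The 5% is per outcome, and the plan gives no rule across its two primary outcomes. With one true null in each and independence, trial-wide error is 1 − (1 − 0.0167)² = 3.3% under Bonferroni and 1 − 0.95² = 9.75% under Shaffer. That difference is real. The bound over all six tests is 6 × 0.05/3 = 10% with either rule, however, and the two agree when all arms are equal. The cross-outcome rule is a separate question that the plan needs to answer whichever rule is used within an outcome.

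The logic also requires two-sided equality nulls. Section 15.3 is worded directionally, and with one-sided nulls two could be true while one is false. The fix must therefore state two-sided tests.

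Finally, the simulation uses unadjusted z-tests on a full 98 per arm, while the plan has covariate-adjusted models and expects 30% dropout. If only 69 per arm were analysed (an assumption, since the ITT population keeps everyone randomized), low vs placebo would be 0.64 under Bonferroni and 0.79 under Shaffer, so the gain persists. Drinking was not simulated; the logic carries over, but the plan already regards its power there as more than sufficient.

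**Conclusion.** The flat 0.05/3 is sound but needlessly conservative for the second and third comparisons. Under the plan's implied 10/28/46%, Shaffer's rule adds just under 10 points for low vs placebo and for both doses vs placebo (0.81 to 0.91), about 15 points for high vs low (0.59 to 0.74) and 23 points for all three (0.43 to 0.66). Under 10/28/28%, both doses vs placebo gains 13 points (0.70 to 0.83). These figures rest on two-sided tests, 98 analysed per arm, and rates of which the 46% and the second 28% are assumptions.

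Two stronger inferences should be resisted. The sample size is not shown to be wrong or reducible: 98 remains right for a comparison that must succeed alone at the first step, and the chance of at least one rejection does not move. Nor is 0.80 a lower bound for every comparison. It holds for 10% vs 28% only; high vs low is below it with or without stepping.

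**What to change.** In 15.4, state for each primary outcome that the three two-sided pairwise tests follow Shaffer's step-down at 5%: if the smallest p-value is at or below 0.05/3, test the other two at 0.05; otherwise stop. Cross-refer to this from both multiplicity statements in 15.5. Holm (0.05/3, 0.05/2, 0.05) is an acceptable simpler choice, with nearly the same gain under 10/28/46% but less under 10/28/28%. An omnibus test followed by 0.05 is not equivalent and should not be substituted.

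Keep 98 per arm. Attach the 0.80 explicitly to 10% vs 28%, and quote the stepwise power for the other claims with their assumed rates, including 0.74 for high vs low. Say that the 5% applies per outcome.

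The cost is a few sentences, fixed before unblinding. Because Bonferroni intervals would no longer correspond to the tests, report unadjusted confidence intervals, labelled as such, alongside adjusted p-values. The change also gives 15.4 the multiplicity rule that it lacks.

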15.4 Subject Populations

The ITT population will be used for the primary analysis and is defined as the subjects who are randomized into the study. The evaluable population is defined as those subjects randomized to the study who completed at least 6 consecutive weeks of maintenance investigational product administration with a dose of at least 50 mg per day for at least 5 days of each 7-day weekly period. The safety population includes all subjects who received at least one dose of investigational product.

Analysis: Data will be summarized with respect to the primary and secondary outcome measures, demographics, and baseline characteristics. In general, quantitative variables will be summarized with standard descriptive statistics (e.g., range, quartiles, means, standard deviations), while frequency tables will summarize categorical variables. Group comparison for quantitative variables will be performed using standard two-sample t-tests or analysis of variance as appropriate. Highly skewed variables may be transformed prior to inferential comparison, or non-parametric methods may be used if needed. Group comparison for categorical variables will be analyzed with two-sample comparisons of proportions, or chi-square tests as appropriate.

The primary efficacy variables will be the PHDD for the drinking outcome and the continuous abstinence rate for the smoking outcome (during the last 4 weeks of treatment, i.e., weeks 15–18 inclusive), respectively. The secondary efficacy variables will be quality of life and measures of alcohol and nicotine craving.

Exploratory outcome variables will include other: 1) measures of drinking severity (i.e., DDD) and abstinence (i.e., percentage of days abstinent; PDA) averaged across either the entire double-blind period or the last 4 weeks of treatment, and 2) smoking measures including the point prevalence abstinence rate and the CO level over either the entire double-blind period or the last 4 weeks of treatment; 3) psychological assessments including measures of nicotine and alcohol withdrawal (WSWS, MOS-Sleep, CIWA-Ar), negative affect (PANAS, CES-D), dependence (FTND), drinking behavior (DrInC) and compliance (BBCET).

The general approach to statistical analyses will be the same as what we utilized in our previous studies.[4, 5] All randomized subjects will be included in the analysis using the intent-to-treat principle. Statistical analyses will be conducted using SAS 9.1 (SAS Institute Inc., Cary, NC).[6]

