Primary Outcomes Analytical Models:

We will use generalized linear models (GLM) to estimate treatment effects on PHDD and logistic regression for abstinence. We will adjust for baseline covariates on the same drinking or smoking variables. For the drinking and smoking variables, that baseline is the averaged value for the 90-day period prior to the screening visit. Other potential covariates shall include age, gender, and ethnicity. We also will consider the treatment period up to the TQD as an additional set of covariates for analyses that focus on the last 4 weeks of treatment. The residuals from our analyses will be checked for normality by computing their skewness and kurtosis and will be checked for homogeneity of variance by plotting them in a histogram and against predicted outcomes. Standard transformations will be employed to improve the distributions when required (i.e., square root or log transformation).

If, however, there is a differential attrition rate (i.e., if dropout is informative), we shall consider other approaches to handle repeated-measures data that can be adopted to obtain valid results.[7, 8]

Exploratory Analytical Models:

We also will use the more advanced two-part random-effects model[9, 10] to analyze the daily drinking and smoking record. Such a model can simultaneously characterize the frequency (odds of daily drinking or smoking being zero) and quantity (number of drinks on a drinking day or number of cigarettes smoked on a smoking day) of drinking and smoking outcomes, respectively. It is more efficient and can tackle non-normality in the drinking or smoking level. We also are interested in trajectory analysis of different treatments over time to capture differences in these outcomes. Such analysis is more clinically intuitive and could be more powerful than the analysis based on endpoint.

The Kaplan-Meier survival method will be used to compare time to achieve continuous abstinence between the treatment groups. Homogeneity between different arms will be tested with the log-rank test. Additionally, we will use the Cox proportional-hazards model to estimate the relative likelihood (i.e., magnitude of the treatment response) between the treatment groups for achieving continuous periods of abstinence. For the Cox regression model, potential confounding variables such as age of onset for alcoholism (less than 26 years old or 26 years and

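### Section 15.5's drinking power and attrition waiver belong to a mixed-model slope test, not to the planned primary GLM on weeks 15–18 PHDD

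*Combined protocol and SAP*

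**What the plan says.** **Drinking power (Section 15.5).** The null hypothesis is "no difference in the declining rate in weekly PHDD between low-dose topiramate, high-dose topiramate, and the placebo group". The effect comes from an earlier multi-site trial, in which "the slope of PHDD for the topiramate group declined faster than that for the placebo group by 0.014 per week" (SE 0.003). Power is taken from an F-test in a mixed model at alpha 0.05/3, and 76 per arm is said to give 80%. Because 98 per arm will be randomized, the section concludes: "Hence, this study will be operating under increased power for the primary efficacy variable on drinking outcome".

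**Attrition (Section 15.5).** "Since we already accounted for dropout in the mixed model for the multi-site study, no additional measure to address the attrition rate is necessary", with the condition "as long as the weekly dropout rate (i.e., not the total dropout) in the present study is similar to that in the previous trial". The weekly rate is given for neither trial. The Abstract (Study Duration) expects 30% dropout, with 206 of 294 completing 18 weeks.

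**Primary analysis (Sections 15.1 and 15.4).** The primary outcomes are PHDD and continuous smoking abstinence, "during the last 4 weeks of treatment, i.e., weeks 15–18 inclusive". The models are: "We will use generalized linear models (GLM) to estimate treatment effects on PHDD and logistic regression for abstinence". On the population: "All randomized subjects will be included in the analysis using the intent-to-treat principle". Repeated-measures alternatives are only to be considered, and only if attrition differs between arms, which the text treats as the meaning of informative dropout. A two-part random-effects model appears under the exploratory models.

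**Smoking power (Section 15.5).** Abstinence of 10% against 28%, read from a named figure of the cited bupropion trial at 18 weeks, with alpha 0.017, gives 98 per arm at power 0.80. This figure sets N = 294.

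**The concern.** The power statement and the planned test concern different quantities. A slope model uses every week a subject contributes, so someone who leaves at week 8 still informs the estimate; that is the only argument offered for making no attrition allowance. A GLM on a weeks 15–18 summary has no value for that subject, and the plan does not say how such a subject is kept in an analysis of everyone randomized. The claim of increased power for the primary drinking variable is therefore unsupported for the test that will be run.

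Two related gaps matter. Section 15.4 equates informative dropout with unequal attrition, but dropout can be informative at equal rates, for instance if one arm loses subjects to side effects and the other to relapse. For smoking, the endpoint that sets N, the calculation is silent on dropout. How subjects without data are handled could then be settled after the data are seen.

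**Working it through.** **1. Reproduce the smoking figure that sets N.** Inputs (Section 15.5): p1 = 0.10, p2 = 0.28, alpha 0.017, power 0.80. Two-sided is inferred because it reproduces the figure. Pooled two-proportion formula, with mean rate p = 0.19:

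- n = [z(α)·√(2p(1−p)) + z(0.80)·√(p1(1−p1) + p2(1−p2))]² / (p2−p1)²
- = [2.387 × 0.5548 + 0.8416 × 0.5400]² / 0.0324 = 97.6, so 98 per arm.

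With alpha unrounded at 0.05/3 it is 99, and power at 98 is 0.80. The figure reproduces with no dropout term.

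**2. What dropout does to smoking power.** n = 98, alpha 0.05/3, 10% v 28%:

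- Rates already count dropouts as smokers, with similar attrition here: power 0.80.
- Completers' rates, with missing counted as smoking: rates are multiplied by (1 − missing fraction). At 10% missing, 9% v 25.2%, power 0.74. At 20%, 8% v 22.4%, power 0.66. At 30%, 7% v 19.6%: Φ[(0.126 × √98 − 2.394 × 0.4802)/0.4719] = Φ(0.207) = 0.58.

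The documents give the source, figure, time point and measure of the rates, but not their denominator.

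**3. Try to reproduce 76 per arm for drinking.** At alpha 0.05/3, 80% power needs a standard error of 0.014/(2.394 + 0.842) = 0.00433. If the standard error scales as 1/√n, then 76 = n₀ × (0.003/0.00433)² = 0.481·n₀, so n₀ is about 158 per arm in the earlier trial. The documents do not give that trial's size, so 76 cannot be checked.

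**4. What the weeks 15–18 comparison would need.** Two-sample comparison, alpha 0.05/3, power 0.80: d = (2.394 + 0.842) × √(2/n), which is 0.462 at n = 98 and 0.551 at n = 69 (70% of 98). With the t distribution these become 0.466 and 0.557. So 80% power needs a difference of 0.47 SD if everyone has data and 0.56 SD if 30% do not, before baseline adjustment.

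**5. Can the plan's inputs settle that?** No: it gives neither an SD nor a mean difference for weeks 15–18. As an illustration only, read 0.014 as a proportion of days per week and assume linear divergence to the mid-window, week 16.5:

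- From the start of treatment: 0.014 × 16.5 = 0.231. 80% power needs an SD of at most 0.231/0.466 = 0.50 (98 per arm) or 0.231/0.557 = 0.41 (69).
- From the target quit date only: 0.014 × 11.5 = 0.161. The SD limits are 0.161/0.466 = 0.35 and 0.161/0.557 = 0.29.

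The answer turns on the SD and on the path of divergence, and the plan states neither for this endpoint.

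**6. Size of the group affected.** 294 − 206 = 88. This is an upper bound on loss through dropout: Section 12.2 lets subjects who stop medication remain in the study, and Section 13.4 allows visits by telephone.

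**The case against.** The best defence is that a repeated-measures primary analysis was intended. Section 15.4 says the general approach follows the previous studies, Section 15.5 shows that one of them used a mixed model, and Section 15.4 speaks of other approaches to repeated-measures data. That makes the intention plausible. It does not name such a model: the only random-effects model for drinking is listed as exploratory. Section 15.3 adds the period after the quit date to the hypotheses, but that is not a slope either.

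A reader might infer that the trial is underpowered for drinking. The documents do not support that. Section 15.4 plans baseline adjustment, which lowers the requirement in step 4. With an assumed baseline correlation of 0.5 (not in the documents), the residual SD is √(1 − 0.25) = 0.87 of the raw SD, and the required differences fall to about 0.40 SD and 0.48 SD. Also, 69 per arm assumes that no non-completer supplies late data.

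A reader might likewise infer that smoking power is really 0.58. That needs completers' rates, which no section indicates. Section 15.4 analyses everyone randomized, and Sections 14.19 and 15.3 require self-report with CO verification, so a subject who has left is most naturally not abstinent. If the planning rates are on that basis, 0.80 stands. What remains is that neither the basis nor the rule is written down.

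**Conclusion.** The point holds as a mismatch between the power statement and the primary analysis. The 80% at 76 per arm, the increased power at 98 and the attrition waiver apply to a mixed-model slope test, on condition of an unstated weekly dropout rate. They do not apply to a GLM on weeks 15–18 PHDD. Power for that endpoint may be adequate; the plan does not show it, because it gives no SD. The requirement of 0.47 SD (98 per arm) to 0.56 SD (69 per arm) rests on two-sided alpha 0.05/3, equal arms and no baseline adjustment.

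For smoking the finding is conditional: 0.80 if the 10% and 28% count dropouts as smokers, about 0.58 at 30% missing if they do not. Nothing here shows that N = 294 is too small. Tying informative dropout to unequal attrition is a separate flaw, and it holds without any numerical assumption.

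**What to change.** 1. Make the primary PHDD analysis a baseline-adjusted mixed model on weekly PHDD in all randomized subjects, with the weeks 15–18 average as the treatment contrast. State that weekly PHDD is calculated over days with TLFB data, and reconcile this with the Abstract, which divides by the number of study days.
2. Label 76 per arm and the attrition sentence as belonging to the slope calculation only. The weeks 15–18 contrast in item 1 is not that slope test either, so restate drinking power for it with a stated difference, SD and dropout. N does not change.
3. Run the informative-dropout sensitivity analysis (the joint models in references 7 and 8) whether or not attrition differs between arms.
4. For smoking, keep all randomized subjects in the denominator and count anyone without verified abstinence in weeks 15–18 as smoking. State whether 10% and 28% are on that basis, and restate power if they are not.

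The cost is SAP wording, a power restatement and a little more analysis, all on data already being collected. The downside is that the stated power may come out less favourable.
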